1. To establish whether robot assisted therapy provides any additional motor recovery for the hand when administered during the subacute stage in a Chinese adult population diagnosed with stroke.
2. To evaluate the feasibility and efficacy of robot-assisted hand rehabilitation in improving arm function abilities in subacute hemiplegic patients.

Outcome evaluation

(A) Fugl-Meyer assessment (FMA) scale (14): The investigators used FMA scale to evaluate sensorimotor recovery of patients with particular attention to the hand and wrist section (maximum score=24) to assess the functional capacity of the affected hand.

(B) The Motricity Index (MI) scale (15): The investigators used MI scale to assess the motor recovery rate of the patients (100% = maximum MI).

(C) Functional Independence Measure scale (FIM) (16): The investigators used FIM to assess the degree of independence and need-of-assistance in basic activities of daily living at enrolment and at the end of the study. FIM is an 18-item ordinal scale rated from 1 (total dependence) to 7 (total independence) per item; 13 items of this scale, the sub-scale Motor- FIM, were used to evaluate motor disability.

(D) Visual analogue scale (VAS) (17): The investigators used VAS (0 extremely simple- 10 extremely difficult) to assess the feasibility of the device in terms of the number of patients who completed the program; side effects (the physiotherapist was required to report any adverse events occurring during the study in regard to the use of the robotic hand); and the level of operator difficulty for the physiotherapist in managing the device.

Intervention

The experimental group will receive 30 minutes robotic training sessions, 3 times per week for a total of 30 sessions supervised by a research assistant. The robotic hand is a passive exoskeleton system, which was developed by the laboratory of the Department of Biomedical Engineering in Chung-Yuan Christian University. Participants will be placed in the robot and practice common hand tasks involving single finger range of motion exercise, grasping, and pinching objects. Immediately following this robot training, these subjects will receive schedule (1-hour sessions, 3 times/week, 30 total sessions) of conventional

[figure not shown]

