therapy from an occupational therapist. An occupational therapist will provide one-on-one individualized programs focused on arm and hand function. Treatment will include function-oriented specific tasks, such as reach, grasp, transport and release of various objects between different targets.

In conventional therapy group, participants will receive an one-hour of one-on-one treatment from an occupational therapist, focusing on arm and hand function. Treatment will include function-oriented specific tasks, such as reach, grasp, transport and release of various objects between different targets. The treatment schedule will parallel that given to the experimental group (1-hour sessions, 3 times/week, 30 total sessions). All patients would undergo basic rehabilitation following the guidelines (18) according to the Bobath concept (19).

Statistical analysis

Statistical analysis was performed with SPSS 22.0 (IBM, USA). The normality of variables was assessed using the Kolmogorov–Smirnov test. Confirmation of matching in initial conditions in co-factors among control and intervention groups was made using Wilcoxon Rank Sum (WRS) tests with continuity correction or Fisher’s exact test (FET), depending on the nature of the variables (categorical, interval or ratio). For each group, improvements in dexterity performance were evaluated using Wilcoxon Sign Rank (WSR) test with continuity correction for paired samples. Comparative differences between control and intervention in these improvements were established using Wilcoxon Rank Sum tests with continuity correction. Cohen’s d effect sizes and the 95% confidence interval for the contrast (continuous data) were further calculated. In all cases, statistical significance threshold was kept at $\alpha = 5\%$.

Steps of experiment

Study participants

(A) Inclusion criteria: Adult patients (>20 years old) with a diagnosis of hemorrhagic or ischemic stroke and who experience severe upper extremity hemiparesis.

(B) Exclusion criteria: severe pain and instability in the wrist of the affected arm, severe cognitive impairment, aphasia, hemispatial neglect, apraxia and joint contractures greater than 20 degrees in the affected hand.

(C) The number of estimated enrollment is thirty-six stroke patients (18 in intervention group and 18 in control control).

References

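### No primary outcome is named: efficacy is tested at an unadjusted 5% on 'dexterity performance', which no listed scale is said to measure

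*Combined protocol and SAP*

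**What the plan says.** The Outcome evaluation section lists four lettered measures and labels none of them primary or secondary.

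- (A) FMA, used "with particular attention to the hand and wrist section (maximum score=24) to assess the functional capacity of the affected hand".
- (B) MI: "The investigators used MI scale to assess the motor recovery rate of the patients".
- (C) FIM, with its 13-item Motor-FIM sub-scale. This is the only measure with stated assessment times (enrolment and end of study).
- (D) A VAS, used for feasibility and operator difficulty.

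The Study objective section names no scale. Objective 1 is "To establish whether robot assisted therapy provides any additional motor recovery for the hand". Objective 2 is "To evaluate the feasibility and efficacy of robot-assisted hand rehabilitation in improving arm function abilities in subacute hemiplegic patients".

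The Statistical analysis section says: "For each group, improvements in dexterity performance were evaluated using Wilcoxon Sign Rank (WSR) test with continuity correction for paired samples". It continues: "Comparative differences between control and intervention in these improvements were established using Wilcoxon Rank Sum tests with continuity correction". It adds that Cohen's d "effect sizes and the 95% confidence interval for the contrast (continuous data) were further calculated". It closes with "In all cases, statistical significance threshold was kept at" 5%. It describes no testing order and no adjustment for multiple tests.

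**The concern.** The plan does contain a between-arm test, an effect size and a confidence interval. What it lacks is the score to which they apply. The word dexterity occurs once, in the analysis text, and no outcome is said to measure it.

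The most natural reading is the FMA hand-and-wrist section, because it is tied to the affected hand and objective 1 concerns hand motor recovery. Three things remain open:

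- whether the FMA analysis uses the total or the sub-score;
- whether MI could carry objective 1, since its description also speaks of motor recovery;
- whether MI, FIM or Motor-FIM could carry the arm-function efficacy part of objective 2.

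Two careful analysts could follow the text and report different main results. If the claim may rest on whichever score is positive, the stated 5% is not the error rate of that claim. The within-arm signed-rank tests add two more 5% tests per score. They do not compare the arms, yet the plan does not say that they are only descriptive.

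**Working it through.** **Inputs from the documents.** 18 patients per arm (Study participants, C); rank sum test with continuity correction; 5% threshold. The plan gives no effect size, SD or power, so its total of 36 cannot be reproduced.

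**Assumptions.** Two-sided testing, because the plan does not state sidedness; normally distributed change scores; no true effect; correlations between scores as shown.

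**Step 1: independent tests as an upper reference.** The chance of at least one false positive among k tests is 1 − 0.95^k.

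- k = 2: 1 − 0.9025 = 9.75%
- k = 3: 14.3%
- k = 5: 22.6%

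**Step 2: the planned test on correlated scores.** Simulation used 200,000 trials per setting, or 100,000 for five scores. The last column counts only false positives that favour the robot, because the Introduction hypothesises that the robot does better.

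| Scores open to a claim | Assumed correlation | Any false positive | Favouring robot |
|---|---|---|---|
| One | – | 4.70% | 2.36% |
| FMA total and hand-and-wrist | 0.7 | 7.94% | 3.92% |
| | 0.8 | 7.64% | 3.86% |
| | 0.9 | 6.88% | 3.39% |
| FMA, MI, FIM | 0.3 | 13.07% | 6.59% |
| | 0.5 | 12.06% | 5.99% |
| | 0.7 | 10.71% | 5.35% |
| Five (adding hand-and-wrist and Motor-FIM) | others 0.3; FMA part-whole 0.7; FIM part-whole 0.9 | 17.38% | 8.84% |
| | others 0.7; FMA part-whole 0.9; FIM part-whole 0.95 | 13.23% | 6.57% |

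The two five-score rows are the extremes of five settings run.

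**Step 3: inflation relative to one score.**

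- Two FMA scores: 6.88/4.70 = 1.46 to 7.94/4.70 = 1.69.
- Five scores, at most: 17.38/4.70 = 3.70.

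**Step 4: cross-check by normal approximation.** Three equally correlated tests give 13.5%, 12.6%, 10.9% and 8.4% at correlations of 0.3, 0.5, 0.7 and 0.9. The rate is above 5% throughout.

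**Step 5: why not keep three co-equal scores with a correction.** The detectable standardised difference is (z for alpha + z for power) × √(2/18), taking 80% power as an assumption.

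- One outcome at 5%: (1.960 + 0.842) × 0.333 = 0.93.
- Three outcomes at 0.05/3 = 1.67%: (2.394 + 0.842) × 0.333 = 1.08.

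For an assumed difference of 0.8, power falls from 67% to 50%. A single primary outcome is the cheaper route in a trial of this size.

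**The case against.** The strongest reply is that dexterity is a single hand construct. FIM is assigned to independence in daily living, so the plan may never have meant it to enter this test. With one hand score, 5% needs no correction. That has force: the three-score and five-score figures are outer scenarios, and the FMA total versus sub-score figure is the one closest to the text. The sub-score is still not designated, however, and that narrow ambiguity alone raises the rate.

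Second, for the two FMA scores the chance of wrongly favouring the robot is 3.4–3.9%, which is below 5%. This is correct. The comparator under two-sided testing is 2.4% for one score, so the increase is real, but it depends on the two-sided assumption.

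Third, the absence of adjustment is inferred from silence, and choosing the score late is a possibility rather than a stated intention. Both are fair. The point is that this document does not prevent it.

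Fourth, one might treat the trial as a pilot. The plan does not call itself one. It sets out to establish added recovery and fixes a significance threshold.

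Finally, choosing FMA hand-and-wrist over MI or FMA total is partly a judgement, so the fix leaves room for the sponsor to choose.

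**Conclusion.** The concern holds. No listed score is designated for the efficacy contrast, and the 5% threshold carries no hierarchy. Taking only the narrowest ambiguity, FMA total versus hand-and-wrist, the false-positive rate rises from 4.7% to 6.9–7.9%, about 1.5–1.7 times. If all five efficacy scores are open to a claim, it reaches 13.2–17.4%, at most 3.7 times. These sizes rest on assumed correlations, assumed two-sided testing and an assumed number of scores. The inflation arises only if efficacy may be claimed on more than one score, which the plan does not exclude. This should be corrected, and a change of wording is enough.

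**What to change.** Replace the dexterity term with one primary outcome: the between-arm difference in change from enrolment to end of study in the FMA hand-and-wrist score (0–24), tested with the planned rank sum test at two-sided 5%. Label FMA total, MI, FIM and Motor-FIM as secondary and supportive, reported with effect sizes and 95% confidence intervals. The VAS stays a feasibility measure. Also state that FMA and MI are assessed at the same two times as FIM, that within-arm signed-rank results are descriptive, and that efficacy rests on the between-arm contrast.

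**Cost.** No change to the tests or sample size. The data collected are also unchanged, provided FMA and MI are already planned at both times, which any improvement score needs. A lone positive secondary score or within-arm p-value can no longer be claimed as efficacy, and the arm-function efficacy part of objective 2 becomes supportive.

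**Floor risk.** Entry requires severe hemiparesis, so some patients may show no change on a hand score. As an illustration only, assume integer change scores with mean 5 and SD 3, and a 1.0 SD greater gain in those robot patients who can change. If 0%, 25% or 50% of each arm shows no change, power is about 80%, 35% or 12%. The documents give no baseline distribution to test this against. If the sponsor expects such a floor, it can name FMA total instead, stating whether that means the upper limb or the whole scale, provided the choice is fixed before outcome data are seen.
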